### 5.1.1 Dose Escalation Procedure

Dose escalation of DS-6157a will be guided by a Bayesian logistic regression model (BLRM) (Neuenschwander et al. 2008) following the escalation with overdose control (EWOC) principle (Babb et al. 1998, Rogatko et al. 2005). The details of the methodology are described in Section 10.7.

Cohorts of 3 to 6 patients will be enrolled and assessed for DLT during Dose Escalation. The first two patients at each dose level in Dose Escalation will start the study treatment (first dose) at least 24 hours apart. Dose escalation decision and enrollment of patients to a new cohort requires completion of DLT evaluation of at least 3 patients treated in the current cohort. Patients who have neither completed the DLT evaluation period with full dose nor experienced a DLT will not be included in the BLRM update. In the event that additional patients in the previous cohort experience a DLT after the enrollment of patients to a new cohort has begun, dose level assignment of the next patient in the study will be based on an updated BLRM using DLT outcome data from all assessed doses thus far, and clinical assessment of the overall safety data by the Sponsor and Investigator(s). The model will also be re-evaluated before enrolment of any additional patients to a cohort if 2 evaluable patients in the cohort experience DLT before the enrollment of the next patient.

CONFIDENTIAL

The next dose level will be chosen by the Sponsor and Investigator(s) based on the dose recommendation by the BLRM as outlined in Section 10.7.3, and clinical assessment of the overall safety data. In addition, any available PK, pharmacodynamics, and efficacy data may be considered for dose escalation decisions. The dose level increase will not be greater than 100% even if the BLRM suggests a dose higher than 100% for next cohort.

The actual number of dose cohorts to be explored in this study will depend on determination of the MTD based on DLTs reported during the DLT evaluation period (Day 1 to Day 21 of Cycle 1 in Dose Escalation). Additional patients may be enrolled at the MTD or any dose levels below the MTD in order to collect sufficient safety and PK data or to characterize safety and PK in specific ethnicities.

For MTD (or RDE if MTD is not observed) determination, the following stopping rules will be implemented for Dose Escalation:

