**For Hepatic Organ Toxicities, a DLT is defined as follows:**

- Grade 4 aspartate aminotransferase (AST) or alanine aminotransferase (ALT) increased
- AST or ALT  $> 3 \times$  ULN if accompanied by Grade  $\geq 2$  blood total bilirubin increased with serum alkaline phosphatase  $< 2 \times$  ULN (based on Hy's law definition)
- In patients without liver metastases, AST or ALT  $> 5 \times$  ULN
- In patients with liver metastases, AST or ALT  $> 5 \times$  ULN, if the baseline level was  $\leq 3 \times$  ULN
- In patients with liver metastases, AST or ALT  $> 8 \times$  ULN, if the baseline level was  $> 3 \times$  ULN

**For Non-Hematologic, Non-Hepatic Major Organ Toxicities, a DLT is defined as all TEAEs of Grade  $\geq 3$  with the following exceptions:**

The following AEs will not be considered DLTs:

- Grade 3 fatigue lasting <7 days
- Grade 3 nausea, vomiting, diarrhea, or anorexia that has resolved to Grade  $\leq 2$  within 3 days with maximal medical management
- Grade 3 isolated laboratory findings not associated with signs or symptoms including alkaline phosphatase (ALP) increased, hyperuricemia, serum amylase increased, and lipase increased, and Grade 3 hyponatremia lasting <72 hours developed from Grade 1 at baseline. Symptomatic Grade 4 events will be considered DLTs unless there is documented evidence that the abnormality is associated with disease progression.

For the following non-hematologic, non-hepatic major organ toxicities, a DLT is defined as:

- Symptomatic congestive heart failure

- Any LVEF decline from baseline leading to discontinuation of study treatment
- Grade  $\geq 2$  ILD or pneumonitis
- Grade 3 skin toxicity lasting  $>7$  days or Grade 4 for any duration
- All other Grade  $\geq 3$  non-hematologic, non-hepatic major organ toxicities will be a DLT

If any of the toxicities listed directly above are observed during the DLT evaluation period, the Investigator, Medical Monitor, and Sponsor will discuss if they are to be classified as DLTs.

Premedication (any treatment administered prior to study drug administration to avoid TEAEs), is prohibited during the DLT evaluation period. However, supportive therapy for the treatment of TEAEs is permitted after DS-6157a infusion (e.g., antiemetics are permitted if nausea and vomiting are observed post-dose but will not be administered prior to dosing to prevent nausea and vomiting during the DLT evaluation period).

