### **Determination of Dose-Limiting Toxicities**

The patient population (DLT-Evaluable Set) used for determination of DLTs will consist of all patients enrolled in Dose Escalation who had a DLT, or who received the full dose of DS-6157a in Cycle 1 and completed the DLT evaluation period. Minimum safety requirements will be met if, during Cycle 1 of treatment, the patient receives the planned total dose of DS-6157a, completes all required safety evaluations, and is observed for at least 21 days following the first dose of DS-6157a. Dose escalation to the next dose level will take into account all the safety data as detailed in Section 5.1.1.

Patients who discontinue treatment early due to PD or withdrawal will be asked to have all end-of-treatment safety evaluations performed as described in the protocol (see Section 7.4). If a patient withdraws from treatment during Cycle 1 due to any reason other than a DLT and does not meet the minimum requirements for inclusion in the DLT-Evaluable Set described above, that patient will be replaced.

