## 5.2 Treatment Duration

DS-6157a will be administered IV on Day 1 of each cycle Q3W. Patients will continue to receive DS-6157a Q3W as long as the patient is deriving benefit from the treatment, until progression of disease (PD) according to RECIST Version 1.1 as assessed by the Investigator, unacceptable toxicity, death, or withdrawal of consent (Section 3.3). Patients may be treated beyond initial radiological progression (according to RECIST Version 1.1) on a case-by-case basis (with agreement from the Medical Monitor), if the Investigator feels that it is in the patient's best interest, the patient re-consents to continue receiving study treatment in a separate consent form, and as long as the patient is deriving benefit from the treatment and all the following criteria are met:

- Absence of clinical symptoms or signs indicating clinically significant disease progression
- No decline in performance status
- Absence of rapid disease progression or threat to vital organs or critical anatomical sites (e.g., CNS metastasis, respiratory failure due to tumor compression, spinal cord compression) requiring urgent alternative medical intervention
- No significant, unacceptable or irreversible toxicities related to study treatment
- Patient agrees to continue protocol-specified assessments and monitoring

Assessments will be performed by the Investigator at screening and every 6 weeks ( $\pm 7$  days) during the first 36 weeks of treatment and every 9 weeks ( $\pm 7$  days) thereafter, as described in the [Assessment Schedule](#) and in Section 7.3. After treatment discontinuation, patients will be evaluated according to follow-up procedures described in Section 7.4.

The **start of the study** is defined as the date when the first patient in the study signs informed consent.

The **end of the study** is defined as the date of the last visit (including all follow-up visits) of the last patient in the whole study.

*CONFIDENTIAL*

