- Patient who meets any of exclusion criteria based on the most recent data, or who experienced ILD of any grade or any other dose modification toxicity event during DS-6157a treatment will not be eligible for IPDE.

IPDE may be conducted up to a dose that is 1 dose level below the dose already established to be safe and tolerable. Dose escalation should not be more than 3 dose levels at a time. The actual dose level will be decided based on the overall individual clinical status and PK profile. A patient may be allowed further IPDE after completing a minimum of another 4 cycles after the first IPDE, as long as the conditions for IPDE are met. AEs arising after IPDE should follow dose modifications/reductions per [Table 2](#), but further re-escalations will be prohibited after such events.

Dose can be delayed for up to 28 days from the planned date of administration. If a patient has a persisting AE/SAE that requires a longer dose delay, then patient will be withdrawn from the study after consulting with Medical Monitor.

Treatment cycles for a patient for whom DS-6157a dosing was temporarily withheld for any reason may have future cycles scheduled based on the date of the last DS-6157a dose. However, the tumor assessments will follow the pre-specified schedules relative to the start of the study treatment (Cycle 1 Day 1).

Investigators may contact the Medical Monitor or designee to discuss questions regarding dose modification or discontinuation of study drug.

All confirmed or suspected coronavirus disease 2019 (COVID-19) infection events must be recorded in the eCRF. Please refer to [Appendix H](#) for additional information on dose modifications.

*CONFIDENTIAL*

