AST/ALT $\geq 3.0 \times$ ULN with simultaneous TBL $>2.0 \times$ ULN	
Delay study medication until drug-induced liver injury can be ruled out.
 
If drug-induced liver injury is ruled out, the patient should be treated accordingly, and resumption of study drug may occur after discussion between the Investigator and Sponsor.
 
If drug-induced liver injury cannot be ruled out from diagnostic workup, permanently discontinue study treatment.
 
Monitor AST/ALT and TBL twice weekly until resolution or return to baseline.

Aspartate aminotransferase (AST) or alanine aminotransferase (ALT)	
Grade 2 ( $>3.0 - 5.0 \times$ ULN if baseline was normal; $>3.0 - 5.0 \times$ baseline if baseline was abnormal)	No action for Grade 2 AST/ALT

Grade 3 (<math>>5.0 - 20.0 \times</math> ULN if baseline was normal; <math>>5.0 - 20.0 \times</math> baseline if baseline was abnormal)
 
In patients without liver metastases and patients with liver metastases and
	
Repeat testing within 3 days. Delay dose until resolved to <math>\leq</math> Grade 1 if baseline <math>\leq 3 \times</math> ULN, otherwise delay dose until resolved to <math>\leq</math> baseline, then:
 
If resolved in <math>\leq 7</math> days from day of onset, maintain dose            If resolved in <math>>7</math> days from day of onset, reduce dose 1

CONFIDENTIAL

baseline level $\leq 3 \times \text{ULN}$	level
Grade 3 ( $>8.0 - 20.0 \times \text{ULN}$ if baseline was normal; $>8.0 - 20.0 \times \text{baseline}$ if baseline was abnormal)  In patients with liver metastases, if the baseline level was $>3 \times \text{ULN}$	Repeat testing within 3 days. Delay dose until resolved to $\leq$ baseline level, then: If resolved in $\leq 7$ days from day of onset, maintain dose If resolved in $>7$ days from day of onset, reduce dose 1 level
Grade 4 ( $>20.0 \times \text{ULN}$ if baseline was normal; $>20.0 \times \text{baseline}$ if baseline was abnormal)	Discontinue patient from study treatment
Total Bilirubin	

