### 11.4 Expedited Reporting by Investigators

The following types of events must be reported by the Investigator in the eCRF within 24 hours of awareness:

- SAEs (See Section 11.1.2 for definition) occurring at any time from the signing of the ICF through the 30-day follow-up period after the last dose of study drug must be reported as SAEs on the eCRF and followed until resolution (with autopsy report if

*CONFIDENTIAL*

applicable). Adverse events classified by the treating Investigator as “serious” require expeditious handling and reporting to the Innovations Safety Department in order to comply with regulatory requirements. Determination of “life-threatening” or “serious” is based on the opinion of either the Sponsor or the Investigator. Additionally, any SAE brought to the attention of an Investigator at any time outside of the time period specified above must be reported immediately to the Sponsor if the event is considered to be drug related.

- All potential ILD/pneumonitis cases should be reported within 24 hours: including both serious and non-serious potential ILD cases (potential ILD is described by the Event Adjudication Site Manual).
- Hepatic events (both serious and non-serious, and clinical laboratory result) which meet the potential Hy’s Law criteria defined as an elevated [ALT or AST]  $\geq 3 \times$  ULN and an elevated total bilirubin  $> 2 \times$  ULN that may occur simultaneously or at different time points during the study, regardless of whether these hepatic events are symptomatic, lead to study drug discontinuation, dose reduction or dose interruption, require corrective treatment, constitute an AE in the Investigator’s clinical judgment. A targeted questionnaire is built within the eCRF to collect relevant additional information for these potential cases. For broad surveillance of hepatotoxicity, hepatic events that meet the biochemical criteria (AST or ALT  $\geq 3 \times$  ULN, TBL  $> 2 \times$  ULN) are included for enhanced data collection.
- Overdose is always serious. By definition an overdose is medically important, which meets the seriousness criterion of important medical event. An overdose can occur with or without an AE. AEs can either be serious or non-serious. Details of the overdose including DS-6157a dosage, clinical course, associated AEs, and outcome must be captured in the narrative form of the eCRF.

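### A narrow band of Cycle 1 liver events that permanently end treatment under Table 2 is not a DLT in Section 5.1.2, so the BLRM normally scores it as tolerated

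*Combined protocol and SAP*

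**What the plan says.** **DLT definition (protocol Section 5.1.2, hepatic list).** The combined item needs three things: AST or ALT above 3×ULN, bilirubin of Grade 2 or more, and low ALP ("blood total bilirubin increased with serum alkaline phosphatase" below 2×ULN, labelled as following Hy's law). The other hepatic items need Grade 4 AST/ALT, or AST/ALT above 5×ULN. The second limit is 8×ULN for patients with liver metastases and a baseline above 3×ULN. A general clause in the same section adds events of Grade 3 or more, unless clearly due to progression or intercurrent illness.

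**Dose modification (Section 6, Table 2, combined AST/ALT and bilirubin row).** The trigger is AST or ALT at or above 3×ULN with simultaneous bilirubin above 2×ULN, at any ALP. Dosing is delayed for a workup, and then: "If drug-induced liver injury cannot be ruled out from diagnostic workup, permanently discontinue study treatment".

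**What reaches the model.** Dosing is once per cycle: "DS-6157a will be administered IV on Day 1 of each cycle Q3W" (Section 5.2). A patient without a DLT who had the full dose and completed the 21 days is evaluable and DLT-free. Otherwise Section 5.1.1 applies: "Patients who have neither completed the DLT evaluation period with full dose nor experienced a DLT will not be included in the BLRM update". Section 5.1.2 provides for replacement: "If a patient withdraws from treatment during Cycle 1 due to any reason other than a DLT" and falls short of the minimum requirements, another patient is enrolled.

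**Nearest comparator (Section 5.1.2, non-hepatic list).** "Any LVEF decline from baseline leading to discontinuation of study treatment" is listed as a DLT, as is Grade 2 or higher ILD. A sentence after that list has the Investigator, Medical Monitor and Sponsor discuss whether events on it are classified as DLTs.

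**The concern.** The two sections use different tests for what looks like the same hepatic signal. Table 2 can stop the drug permanently because it may be injuring the liver, while 5.1.2 records no dose-limiting event. The discussion sentence refers to the list directly above it, which is non-hepatic, so it gives the study team no route to classify this event as a DLT.

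DLT yes/no is the only patient outcome in the BLRM, and Section 1.2 names hepatotoxicity, with ILD, as an important potential risk. At stake are the model's recommended next dose and the estimated MTD, both of which would rest on a cohort recorded as cleaner than it was.

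**Working it through.** **Step 1: is there a gap?** Take normal baselines and a Cycle 1 event with AST 4×, bilirubin 2.5× and ALP 2.5×ULN.

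- Table 2 combined row: 4 ≥ 3 and 2.5 > 2, so it is triggered.
- Combined DLT item: fails, because ALP is not below 2×ULN.
- Transaminase items: fail, because 4 is not above 5 and not Grade 4.
- General clause: fails. By the grade limits printed in Table 2, AST above 3 to 5×ULN and bilirubin above 1.5 to 3×ULN are both Grade 2.

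The same event with ALP 1.5×ULN is a DLT, so ALP alone decides.

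**Step 2: how wide is it?** With normal baselines the band is AST/ALT 3 to 5×ULN, bilirubin above 2 to 3×ULN and ALP at or above 2×ULN. With liver metastases and baseline AST/ALT above 3×ULN, the AST/ALT band runs to 8×ULN. It is bounded on several sides:

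- Bilirubin above 3×ULN is Grade 3 and can count under the general clause.
- ALP above 5×ULN is Grade 3 and may count, although isolated asymptomatic Grade 3 ALP is an exception.
- A liver diagnosis graded 3 or more, recorded in place of the laboratory values (Section 11.5), would count.
- The workup must fail to exclude DILI, and the event must not be clearly due to progression or intercurrent illness.

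**Step 3: how is the patient scored?** Cycle 1 has one infusion. Sections 3.3 and 7.4.2 require at least 30 days of adverse-event follow-up after the last dose, which covers the 21-day window. The usual result is therefore evaluable and DLT-free. The patient is left out only if observation or required evaluations are not completed.

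**Step 4: what does one uncounted event do?** Inputs, from Section 10.7 and Appendix G:

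- Model: logit π(d) = ln α + β ln(d/9.6).
- Prior: independent normals for ln α (mean −1.125, SD 1.373) and ln β (mean −0.308, SD 0.778).
- Next dose: highest P(16% < π ≤ 33%) among doses with P(π > 33%) below 25%, with an increase of at most 100%.
- Doses: 1.6, 3.2, 4.8, 6.4, 8.0 and 9.6 mg/kg.

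The posterior was integrated on a 1201 × 1201 grid over ±6 SD.

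*Reproduction first.* Fifteen of 17 Table 3.1 scenarios tested match, including the six used here (1.1, 2.1, 1.2, 1.13, 1.3, 1.4). The two misses lie at the 25% limit. In scenario 1.6 the grid gives 24.7% at 8.0 mg/kg and allows it, but the table prints 6.4. In scenario 1.19 it gives 25.1% at 4.8 and bars it, but the table prints 4.8.

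*Results.* Earlier cohorts are 0/3. Each percentage is P(π > 33%) at the higher dose.

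| Current dose (higher dose) | 0/3 | 1/3 | 1/4 | 1/5 | 1/6 | 2/6 |
|---|---|---|---|---|---|---|
| 1.6 (3.2) | next 3.2; 5.7% | next 1.6; 34.4% | next 1.6; 26.8% | next 3.2; 20.9% | next 3.2; 16.4% | next <1.6 (26.6% at 1.6) |
| 3.2 (6.4) | next 6.4; 7.3% | next 4.8; 29.7% | 24.7% | next 6.4; 20.7% | next 6.4; 17.3% | next 3.2; 40.9% |
| 6.4 (9.6) | next 9.6; 8.5% | next 8.0; 28.9% | 24.0% | next 9.6; 20.0% | next 9.6; 16.7% | next 6.4; 38.2% |

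- *Cohort of 3:* the uncounted event moves the recommendation up one provisional level at each step.
- *Cohort of 4:* it changes the 1.6 mg/kg step. At the other two, 24.7% and 24.0% are too near the limit to call, given the misses above.
- *Cohort of 5 or 6:* one event alone changes nothing.
- *Cohort of 6 with one ordinary DLT already counted (1/6 against 2/6):* the next dose is 3.2 instead of stopping, 6.4 instead of 3.2, or 9.6 instead of 6.4. The two-DLT re-evaluation in Section 5.1.1 is also not triggered.

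**The case against.** The ALP condition is deliberate: it is the stated Hy's law definition, and a raised ALP may point to cholestasis or liver metastases. DLT rules and Table 2 are not meant to coincide. Anemia of Grade 3 or more requiring transfusion is a DLT, yet Table 2 maintains the dose after Grade 3 anemia resolves. No section says that every treatment-ending event must be a DLT. This stands against any claim of contradiction. It does not explain why an event that the protocol stops as possible drug injury should enter the model as tolerated.

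The safeguards are also real. Potential Hy's law events are reported with no ALP condition: "The following types of events must be reported by the Investigator in the eCRF within 24 hours of awareness" (Section 11.4). The joint safety team looks for signals at least monthly (Section 10.9). Next dose, final MTD and RDE all rest on more than the model (Sections 5.1.1 and 5.1.3, Appendix G). These can correct the decision but not the model input.

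Three stronger readings are tempting, and the documents do not support them:

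- *Patients will be overdosed.* The error is in the model's recommendation and the estimated MTD. The people choosing the dose still see the event.
- *Such patients routinely drop out of the BLRM.* The 30-day follow-up makes that unlikely.
- *Section 5.1.2 automatically counts other treatment-ending events.* The LVEF and ILD items are themselves subject to case-by-case discussion, so a mandatory hepatic rule would be stricter than its precedents.

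**Conclusion.** The gap is real and narrow. A Cycle 1 hepatic event in the band above can end treatment permanently because DILI cannot be excluded, yet it is not a DLT and cannot be discussed as one. The BLRM normally scores it as tolerated.

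Its size is one provisional dose level for one event in a cohort of 3, the minimum for an escalation decision. The effect is smaller or uncertain with 4 patients, and absent with 5 or 6 unless another DLT is counted.

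This rests on the printed prior, DLT-free earlier cohorts, the Appendix G doses, and reading the discussion sentence as limited to the non-hepatic list. If 12.8 mg/kg were also offered (an assumption; the Figure 1 footnote allows higher doses), the 6.4 mg/kg step would be 12.8 instead of 8.0 with 3 patients, and 12.8 instead of 9.6 with 4 or 6. The documents give no frequency for these events, so the figures show what one event could do, not how often it would occur. Minor severity; a cheap improvement.

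**What to change.** Add one item to the hepatic list in Section 5.1.2:

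*AST or ALT ≥3×ULN with simultaneous total bilirubin >2×ULN, regardless of ALP, with onset in the DLT evaluation period (and worsened from baseline if the baseline already exceeds these limits), leading to permanent discontinuation under Table 2 because drug-induced liver injury cannot be ruled out.*

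Extend the existing discussion sentence to this item, so that it is handled like LVEF decline and Grade 2 or higher ILD. Keep the Hy's law item and the progression/intercurrent-illness exclusion. The baseline clause is needed because Section 3.1 admits AST/ALT up to 5×ULN with liver metastases and bilirubin up to 3×ULN with Gilbert's syndrome.

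If a workup is open at an escalation decision, the same group sets a provisional classification, and the BLRM is updated when the workup closes. No cohort need wait. Section 6 gives a natural outer limit: "Dose can be delayed for up to 28 days from the planned date of administration". With Cycle 2 due on Day 22, that is Day 22 + 28 = Day 50. Re-check Cycle 1 hepatic events already reported under Section 11.4.

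The cost is a short amendment and that re-check, with no new data or patients. The downside is the same shift in reverse: an occasional cholestatic or metastasis-related event may be counted and hold the dose one level lower in a cohort of 3. Two such events in 6 patients at 1.6 mg/kg would give a stop recommendation (26.6%; Table 3.1 scenario 2.6). The worsening condition, the exclusion and the discussion step limit this.

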If these assessments are performed within 72 hours of initiation of treatment, they do not need to be repeated on Cycle 1 Day 1 with the exception of the ECOG performance status, an abbreviated physical examination, vital signs, and triplicate ECG that need to be performed prior to the administration of study treatment on Cycle 1 Day 1, as is the case for safety labs, if not done within 72 hours of treatment. Tumor assessments (scans) must be performed  $\leq 28$  days prior to initiation of treatment. Tests for HIV infection, hepatitis B, and hepatitis C must be performed at screening.

- b Physical examinations including the measurements of height (screening only), weight, and skin assessments will be done at screening, on Days 1, 8, and 15 of Cycles 1 and 2, on Day 1 of each subsequent cycle prior to treatment, at the end-of-treatment (EOT) visit, and at the 30-day safety FU visit. ECOG performance status will be assessed at screening, on Day 1 of each cycle prior to treatment, at the EOT visit, and at the 30-day safety FU visit. Skin assessments will include physical examination, dermatological consult (if necessary), and/or skin biopsy as per dermatologist / Investigator's clinical judgment. Vital signs (systolic and diastolic blood pressure, SpO2, body temperature, and pulse rate) are checked at every visit prior to blood work and/or administration of treatment and at the discretion of the Investigator. For subsequent cycles, all Day 1 assessments will have a 48-hour window prior to treatment administration. At the discretion of the investigator, vital signs may be done more than 10 minutes after blood draws other than PK, but prior to administration of treatment.

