- c Triplicate 12-lead ECGs will be done at the time points as outlined in Section 7.5 and whenever the Investigator deems it necessary. A single ECG will be performed on EOT. For each set of triplicate ECGs, three standard resting 12-lead ECGs will be obtained not more than three minutes apart each from the previous ECG. ECGs will be obtained after the patient has been resting quietly in semi-supine or supine position for at least 5 minutes before the first ECG and during the triplicate. When ECG and PK assessments coincide, ECGs must be done within 10 minutes before the scheduled PK sample. When ECG and blood draws other than PK coincide, ECGs should be done before these blood draws, however these blood draws (other than PK) may be taken more than 10 minutes after ECGs, or ECGs may be done more than 10 minutes after these blood draws (other than PK). Parameters to be included are: Heart Rate; RR, PR, and QT intervals; QRS duration; ECG body position; interpretation of ECG. Depending on the emerging ECG data during dose escalation, ECGs may be transmitted to a central reading vendor, as an option.
- d Echocardiogram (ECHO) or multi-gated acquisition scan (MUGA) to be performed at screening (within 28 days before the start of treatment), within  $\pm 3$  days of Day 1 of Cycle 2, then within 7 days before treatment on Day 1 of Cycles 5, 8, and every 3rd Cycle thereafter, and within 7 days before the EOT visit (unless ECHO or MUGA has been done within 3 weeks before the EOT). The Investigator may order unscheduled ECHO or MUGA at more frequent intervals if indicated. The LVEF assessment method used at screening should also be used throughout the study.
- e Pregnancy tests are mandatory for women of child-bearing potential within 7 days of starting study treatment (serum), on Day 1 of each cycle (except Cycle 1) (urine dipstick) prior to treatment, and at the EOT treatment (urine dipstick or serum). A positive dipstick pregnancy test must be confirmed by a serum beta human chorionic gonadotropin ( $\beta$ -HCG) pregnancy test.
- f An eye examination performed by an ophthalmologist includes a visual acuity test, slit lamp examination, tonometry, and fundoscopy at screening, EOT, and as clinically indicated.

*CONFIDENTIAL*

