### 5.1.2 Dose-Limiting Toxicity

Toxicity will be assessed using the NCI [CTCAE Version 5.0](#).

A DLT is defined as any TEAE that occurs during the DLT evaluation period (21 days starting from Cycle 1 Day 1), excluding toxicities clearly related to disease progression or intercurrent illness, that are Grade  $\geq 3$  according to the NCI [CTCAE Version 5.0](#), with the exceptions defined below.

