- Coagulation (PT, aPTT or PTT and INR)

If these assessments are performed within 72 hours of initiation of treatment, they do not need to be repeated on Cycle 1 Day 1 with the exception of the ECOG performance status, an

*CONFIDENTIAL*

abbreviated physical examination, vital signs, and triplicate ECGs. ECHO or MUGA, and tumor assessments (scans) should be performed  $\leq 28$  days prior to initiation of treatment. Tests for HIV infection, hepatitis B, and hepatitis C must be performed at screening. For subsequent cycles, all Day 1 assessments will have a 48-hour window except for ECHO/MUGA, which will have a 3-day window at Cycle 2 and a 7-day window for subsequent cycles.

Relevant medical history and concomitant medications present at study entry and/or during screening that are relevant to the patient's safety during the study as judged by the Investigator will be recorded in the electronic case report form (eCRF) (see Section 5.3 for details on concomitant medications).

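### A discontinuation-level LVEF decline is a DLT on Days 1–21, but the first scheduled on-treatment ECHO/MUGA may fall after Day 21 and after dose 2

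*Combined protocol and SAP*

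**What the plan says.** Section 5.1.2 names as a DLT "Any LVEF decline from baseline leading to discontinuation of study treatment". A DLT is defined there as "any TEAE that occurs during the DLT evaluation period (21 days starting from Cycle 1 Day 1", subject to listed exceptions. Section 5.1.1 bases the number of dose cohorts on "DLTs reported during the DLT evaluation period (Day 1 to Day 21 of Cycle 1 in Dose Escalation". Table 2 in Section 6 requires permanent discontinuation for LVEF below 40% or an absolute drop of more than 20 points. For LVEF of 40–45% with a 10–20 point drop, it requires interruption and a repeat scan within 3 weeks, with discontinuation if there is no recovery.

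The Assessment Schedule grid shows ECHO/MUGA at screening and then in the Cycle 2 Day 1 column, with nothing under Cycle 1. Footnote d sets the timing as within ±3 "days of Day 1 of Cycle 2, then within 7 days before treatment on Day 1 of Cycles 5, 8", and every third cycle after that. The scan must therefore precede treatment from Cycle 5 on, but not at Cycle 2. Section 7.2 says that "all Day 1 assessments will have a 48-hour window except for ECHO/MUGA, which will have a 3-day window at Cycle 2", without saying before or after. Footnote b gives the direction of the general rule: "For subsequent cycles, all Day 1 assessments will have a 48-hour window prior to treatment administration".

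To be DLT-evaluable without a DLT, a patient must in Cycle 1 receive the full dose and be one who "completes all required safety evaluations, and is observed for at least 21 days following the first dose of DS-6157a" (Section 5.1.2). On delays, Section 6 says: "Dose can be delayed for up to 28 days from the planned date of administration".

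**The concern.** The DLT list contains an event that needs imaging to detect unless it causes symptoms, and the schedule does not ensure that the imaging is done while the event can still count. Evaluability does not close the gap. It asks for the safety evaluations required in Cycle 1, and the grid lists the scan under Cycle 2. A patient can therefore enter the Bayesian logistic regression model (BLRM) as evaluable and DLT-free with no LVEF measurement after baseline.

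Two things are at stake. Whether the same asymptomatic decline enters the BLRM, and so the 25% overdose limit, can depend on which compliant day the scan was booked. And a patient who already meets a stop or interrupt row of Table 2 may receive the second dose before anyone looks. The second point also applies in Part 2, where no DLTs are assessed.

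**Working it through.** The plan states no figure here, so the check is a day count.

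**Inputs.** Cycle length is 21 days (Section 7.1), with dosing on Day 1 of each cycle (Section 5.2). The DLT window is Days 1–21 (Sections 5.1.1 and 5.1.2). The scan window is Cycle 2 Day 1 ± 3 days (footnote d). The maximum dose delay is 28 days (Section 6).

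**Nominal schedule.** Cycle 2 Day 1 = 1 + 21 = Day 22. The scan window runs from 22 − 3 = Day 19 to 22 + 3 = Day 25, which is 7 days.
- Inside the DLT window: Days 19, 20, 21, so 3 of 7.
- Outside: Days 22, 23, 24, 25, so 4 of 7.
- After the day of dose 2: Days 23, 24, 25, so 3 of 7.

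Day 22 is borderline. A scan taken that day before dosing reflects dose 1 only, and evaluability speaks of at least 21 days after the first dose. If the DLT window is read as running through Day 22, 3 of 7 days are outside.

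**Cycle 2 delayed by d days.** The scan window becomes Days 19 + d to 25 + d. Days inside the DLT window = max(0, 21 − (19 + d) + 1) = max(0, 3 − d).

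| Delay d | Scan window | Permitted days within Days 1–21 |
|---|---|---|
| 0 | 19–25 | 3 |
| 1 | 20–26 | 2 |
| 2 | 21–27 | 1 |
| 3 | 22–28 | 0 |
| 28 | 47–53 | 0 |

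The grid itself prints +2 days for Cycle 2 Day 1, so the d = 1 and d = 2 rows can arise without any toxicity delay.

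**Section 7.2 read as pre-dose only.** The window is Days 19–22, 4 days. One (Day 22) is outside Days 1–21 and none follows the day of dose 2.

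**What one DLT can do to the model.** In Appendix G, Table 3.1, after 0/3 at 1.6 mg/kg and 0/3 at 3.2 mg/kg, 0/3 at 6.4 mg/kg leads to 9.6 mg/kg next (scenario 1.3), while 1/3 leads to 8.0 mg/kg (scenario 1.4). This holds for any single DLT. It says nothing about how often an LVEF decline would be that DLT.

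**The case against.** The strongest reply is that little depends on this. Symptomatic heart failure is its own DLT, and footnote d allows unscheduled scans when indicated. The next dose is chosen on overall safety data as well as the BLRM (Section 5.1.1 and Appendix G, Section 3.1), and the final MTD takes in safety from later cycles (Section 5.1.3). Table 2 stops the patient whenever the drop is found. LVEF decrease is listed among other potential risks (Section 1.2) and is not an adverse event of special interest (Section 11.11). The cardiac changes in Section 1.1.2 were in two monkeys at the lethal dose of the free payload, and the heart is not among the organs listed as affected by DS-6157a itself. All of this stands and limits the weight of the point. None of it puts a silent decline into the model or ahead of dose 2.

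A reader might infer more than the documents support:
- That 4 of 7 is a chance of missing an event. It counts permitted days, and nothing shows how sites book within them.
- That Section 7.2 contradicts footnote d. Both say 3 days; Section 7.2 leaves the direction open. The pre-dose reading comes only from borrowing footnote b. This is an ambiguity.
- That doses 3 and 4 are given with no scan before them. The Cycle 2 scan precedes both; they lack only a new one.
- That escalation should wait for the repeat scan in the LVEF 40–45% row. From a Day 22 scan that could run to 22 + 21 = Day 43, a real cost for an event of unknown frequency.

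One might also argue that a decline seen on Day 23 occurred earlier and so still qualifies. But Section 5.1.1 speaks of DLTs reported in the window, and the discussion clause in Section 5.1.2 covers toxicities observed in it. After dose 2, the two doses can no longer be separated.

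Finally, version 6.0 says that a full analysis of the escalation data is under way (Section 1.2), so a late change could leave cohorts assessed under different rules. That is a reason to apply it to new patients only and to report which rule each cohort followed.

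**Conclusion.** The point holds as a gap between the DLT definition and the scan schedule. On the nominal schedule, 4 of 7 compliant scan days miss the literal DLT window (3 of 7 if Day 22 is accepted) and 3 of 7 follow dose 2. With a Cycle 2 delay of 3 or more days, no compliant day is in the window. The counts rest on the stated Day 1–21 window, a 21-day cycle and footnote d as written.

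The practical effect is confined to asymptomatic declines first seen on a late scan. These would reach overall safety review but not the BLRM posterior. Without an LVEF event rate, the number of DLTs affected cannot be estimated, and the documents do not support a claim that escalation is unsafe. The change is worth making because it only moves an existing scan and follows the rule that footnote d already uses from Cycle 5.

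**What to change.** 1. **Footnote d.** Replace the two-sided Cycle 2 window with: 'within 3 days before the Cycle 2 dose, read before dosing' (nominally Days 19–22). State the same direction in Section 7.2.
2. **Part 1 only, Cycle 2 delayed or not given.** Do the scan by Day 22, using the existing Day 22 PK/ECG visit where it applies (delay of 3 or more days, or treatment not continuing). State that this scan satisfies footnote d, with a repeat before dose 2 only if clinically indicated.
3. **Sections 5.1.1 and 5.1.2, both.** State that this pre-dose-2 scan is part of the DLT evaluation, and that a decline on it meeting the permanent-discontinuation row of Table 2 counts as a Cycle 1 DLT even if read on Day 22. Changing only one section would leave the other's Day 21 limit in conflict.
4. **LVEF 40–45% row.** Do not hold escalation for the repeat scan. If the repeat leads to discontinuation, count it and update the BLRM then, as Section 5.1.1 already does for late DLTs in a previous cohort.

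**Cost.** No extra scan is needed on the nominal schedule. The booking window narrows from 7 days to 4, and the result must be available before dosing. A separate trip is possible if the scan cannot be done on the dosing day, because the grid has no visit between Days 15 and 22; Part 1 patients in Japan are in hospital to Day 21 anyway. A delayed patient may need a second scan if clinically indicated.
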